4.5 Risks and benefits

Appropriate eligibility criteria, as well as specific dose modification and stopping rules, are included in this protocol. Recommended guidelines for prophylactic or supportive management of study-drug induced adverse events are provided in [Section 6.5.1](#). The risk to patients in this trial may be minimized by compliance with the eligibility criteria and study procedures, as well as, close clinical monitoring, and, protocol-defined ruxolitinib dose modifications guidelines and treatment discontinuation criteria. There may be unforeseen risks with ruxolitinib which could be serious. Refer to the most recent [[Investigator Brochure](#)].

As outlined previously, the potential benefit of ruxolitinib for alloSCT patients with cGvHD is based on published pre-clinical and clinical data. Important risks of treatment with ruxolitinib based on the myeloproliferative neoplasms (MPN) clinical development and post-authorization experience to date include myelosuppression (thrombocytopenia, anemia and leukopenia), infections (including tuberculosis (TB), progressive multifocal leukoencephalopathy (PML), hepatitis B reactivation and other opportunistic infections), bleeding and non-melanoma skin cancers (NMSC). Additionally, in patients with hepatic and renal impairment, Area under the Curve (AUC) and half-life of the metabolites of ruxolitinib increased, and hence, these subjects should be carefully monitored and may need to have their dose reduced to avoid dose-related adverse drug reactions. These risks will be monitored closely and mitigated throughout this study as these risks are also common in the alloSCT setting particularly patients with cGvHD. No substantial additional risk for subject safety due to the SARS-CoV-2 virus and the COVID-19 pandemic has been identified at this time and therefore the benefit-risk assessment remains unchanged.

Myelosuppression

Myelosuppression is a common occurrence in alloSCT patients, is commonly experienced effect from cGvHD. Case series in acute and chronic GvHD have identified worsening of myelosuppression in approximately 10% to 20% of GvHD patients treated with ruxolitinib at doses ranging 5-10 mg orally BID spanning several months ([Zeiser et al 2015](#)). This was managed with dose reduction of ruxolitinib to 5 mg orally BID and required holding ruxolitinib in some patients whose absolute neutrophil count (ANC) dropped below 500/mm³.

Administration of hematopoietic growth factors will be allowed per Investigator judgement.

Bleeding

Hemostatic disturbances are common in patients undergoing alloSCT and have a significant impact on morbidity and mortality. Ruxolitinib dose adjustment or dose holding will be based on platelet count (see [Table 6-5](#)), and platelet transfusions may be given as clinically indicated.

Use in patients with hepatic impairment

As the liver could be one of the organs involved in cGvHD pathophysiology, elevated liver function tests (LFTs) including bilirubin and aspartate aminotransferase (AST)/alanine aminotransferase (ALT) cannot be used as a parameter to exclude treatment-naive cGvHD or SR-cGvHD patients or determine starting dose. Diagnostic evaluation and management of hepatic impairment in treatment-naive cGvHD or SR-cGvHD patients treated on this study will follow institutional guidelines. Guidelines for the required diagnostic tests for ruxolitinib induced liver impairment are outlined in [Section 6.5.2.1](#).

Use in patients with renal impairment

Renal impairment is a common occurrence in patients with treatment-naive cGvHD or SR-cGvHD due to episodes of mild dehydration attributable to GI involvement in the outpatient setting causing decreased oral intake as well as concurrent administration of CNI. AlloSCT patients with severely impaired renal function are excluded from enrollment. Diagnostic evaluation and management of renal impairment in treatment-naive cGvHD or SR-cGvHD patients will follow institutional guidelines.

Infections

Serious bacterial, mycobacterial, fungal, viral and other infections have occurred in MPN patients treated with ruxolitinib. Actions to minimize the risk of serious infections in treatment-naive cGvHD or SR-cGvHD patients will follow standard alloSCT guidelines including close monitoring of clinical signs and symptoms of infection, their prompt recognition and treatment. Management of any active viral infection and viral prophylaxis will follow local transplant program guidelines and viral load titer data will be documented when results are available.

Tuberculosis

Subjects in this study will be monitored for any clinical signs and symptoms of active tuberculosis (TB) infection, and appropriate treatment provided. Skin testing for TB will not be performed in this study of alloSCT subjects as this assessment is non-informative due to anergy.

Progressive Multifocal Encephalopathy

Progressive multifocal leukoencephalopathy (PML) is a rare complication in alloSCT recipients. The median time from transplantation to symptom onset has been reported as 11 months, while median time to symptom onset has been notably shorter in other viral encephalitis in this population. These other viral entities, including human herpes virus (HHV-6), herpes simplex virus (HSV), epstein-barr virus (EBV), CMV, hepatitis B virus (HBV), hepatitis C virus (HCV) and varicella zoster (VZV), have been reported with a median time to symptom onset post-hematopoietic cell transplantation (HCT) of between 3 and 8 months, respectively. The incidence of PML in the HCT population is significantly less than in patients with human immunodeficiency virus (HIV), with comparative incidence rates of 35.4 vs. 130 per one-hundred thousand person years, respectively ([Kaufman et al 2014](#)). Actions to minimize the risk of PML in treatment-naive cGvHD or SR-cGvHD patients will follow standard alloSCT

guidelines including close monitoring of any clinical signs of progressive focal neurological symptoms, with prompt diagnostic work up and treatment.

Non-melanoma skin cancers

Non-melanoma skin cancers (NMSCs), including basal cell, squamous cell, and Merkel cell carcinoma have been reported in MPN patients treated with ruxolitinib. Skin cancer incidence is increased in alloSCT patients vs. the general population, including increased risk of basal cell carcinoma (BCC), squamous cell carcinoma (SCC), and malignant melanoma occurring late, generally 10-15 years after transplant ([Omland et al 2016](#)). Any occurrence of skin cancers will be monitored throughout this study.

Long-Term Follow-Up

Long-term side effects after alloSCT include non-malignant organ or tissue dysfunction, changes in quality of life, infections related to abnormal immune reconstitution and secondary cancers. Different categories of secondary malignancies can occur after alloSCT, including: post-transplant lymphoproliferative disorders, late relapse of the primary disease, donor-type secondary leukemia/other malignancy and de novo solid tumors ([Mohty and Mohty 2011](#)). Second primary malignancy rates for treatment-naive cGvHD and SR-cGvHD patients will be assessed during long-term follow up after transplant and will be compared with relevant epidemiologic data.

Safety in pediatric patients: In a Phase I study, ruxolitinib with BID continuous oral dosing in children aged 2.4 to 21.4 (median 14.4) years with refractory/recurrent solid tumors (ST) and hematologic malignancies was well tolerated and showed similar pharmacokinetics to those in adults. No maximum tolerated dose was reached and the recommended dose for continuous BID oral administration was 50 mg/m²/dose ([Loh et al 2015](#)).

Administration of ruxolitinib in juvenile rats resulted in fractures and reduced bone growth (diameter and/or lengths) at an exposure of 3.9 $\mu\text{M}^*\text{h}$ (1211 ng*h/mL) or $\geq 0.5 \mu\text{M}^*\text{h}$ (150 ng*h/mL) based on unbound AUC, respectively.

Based on the analysis of the available data bone effects have been observed in very young rats (human equivalent age of birth) but not in adult animals (human equivalent age of ≥ 12 years). Potential impact on skeletal growth is projected to be impacted by both the extent of exposure and the stage of skeletal development in children, with the greatest effect on those less than 2 years of age, and proportionally greater in those children less than 1 year of age. Negative impacts on skeletal development are judged to be reversible, but post-treatment bone development may not fully compensate for the retardation occurring before the skeleton has matured and further growth ceases. The impact of this potential effect on subsequent growth should be considered relative to the therapeutic effect desired.

Besides the bone effects / growth retardation, the toxicity profile in juvenile rats was comparable to that observed in adult rats. Please refer to the most recent version of the [[Investigator Brochure](#)] for more details.

Supportive published data in pediatric patients: Although no existing clinical data is available among pediatric GvHD patients treated with ruxolitinib, there are several independent published reports suggesting no significant toxicities in this population.

Khandelwal P et al ([Khandelwal et al 2017](#)) described a retrospective clinical experience of 13 pediatric patients of median age 8.5 years (range, 1.6 to 16.5) who received ruxolitinib for steroid refractory acute GvHD, administered orally at 5 mg twice daily for children \geq 25 kg or 2.5 mg twice daily if $<$ 25 kg. Adverse effects in 13 patients included grade 2 to 4 elevated alanine aminotransferase (n=7), grade 3 to 4 neutropenia (n=5) and grade 4 thrombocytopenia (n=3). No patients experienced life-threatening bleeding. All observed adverse effects resolved after discontinuation of ruxolitinib.

Another recent analysis in 22 SR-GvHD (acute and chronic) pediatric patients aged 5 months to 18 years treated with ruxolitinib dosing planned as noted in Khandelwal P et al., showed high overall response rate in acute GvHD (n=13) and chronic GvHD (n=9), of 77% and 89% respectively ([Khandelwal et al 2017](#)). There were 54%, 18% and 13% infections caused by virus, bacteria and fungi, respectively.

Schoettler M et al, ([Schoettler et al 2019](#)) described a single center experience of treating patients aged 7 to 21 years (n=5) with steroid refractory bronchiolitis obliterans syndrome (SR-BOS), chronic GvHD of the lungs with ruxolitinib. Of 5 patients, ruxolitinib was steroid sparing in 4 patients with an evaluable response; 3 were able to stop steroids, and 1 weaned significantly. Four patients tolerated ruxolitinib with no adverse effects and one patient (treated for 4 months with ruxolitinib) had a grade 3 fungal infection (occurred after months of steroid treatment, not directly attributed to ruxolitinib) and had to discontinue ruxolitinib due to infection.

In addition, in isolated reports, ruxolitinib has been used for treating children with various conditions including severe juvenile dermatomyositis ([Aeschlimann et al 2018](#)), chronic mucocutaneous candidiasis ([Bloomfield et al 2018](#)), polycythaemia vera-associated Budd-Chiari syndrome ([Coskun et al 2017](#)), Philadelphia like acute lymphoblastic leukemia ([Ding et al 2018](#)), vasculopathy associated with TMEM173-activating mutations ([Frémont et al 2016](#)) and life-threatening autoimmune cytopenias and chronic mucocutaneous candidiasis ([Weinacht et al 2017](#)).

Besides the bone effects / growth retardation, the toxicity profile in juvenile rats was comparable to that observed in adult rats. Please refer to [\[Investigator Brochure\]](#) for more details.

Adolescent female patients of child bearing potential must be informed that taking the study treatment may involve unknown risks to the fetus if pregnancy were to occur during the study, and agree that in order to participate in the study they must adhere to the contraception requirements outlined in the exclusion criteria. If there is any question that the subject will not reliably comply, they should not be entered or continue in the study.

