This open-label, single-arm, Phase II multi-center study will investigate the activity, pharmacokinetics and safety of ruxolitinib added to the subject's immunosuppressive regimen among infants, children, and adolescents aged ≥ 28 days to < 18 years old with either moderate to severe treatment-naïve cGvHD or SR-cGvHD. Approximately 42 subjects will be enrolled in this study. Subjects will be grouped according to their age as follows: Group 1 includes subjects ≥ 12 y to < 18 y, Group 2 includes subjects ≥ 6 y to < 12 y, Group 3 includes subjects ≥ 2 y to < 6 y, and Group 4 includes subjects ≥ 28 days to < 2 y. Subjects will remain in the age group throughout the study based on the age at the time of start of treatment. Enrollment initiation into the youngest age group, Group 4, will be subject to the availability of data in this age group from study [CINC424F12201], as well as a review of available PK, safety, and activity data generated from Groups 1 to 3 in the current study, in consultation with the data monitoring committee (DMC) and a final decision by the Sponsor. At least 5 evaluable subjects per Group are needed for the primary analysis in Groups 1, 2 and 3. No minimum number of evaluable subjects are needed in Group 4.

[figure not shown]
After a screening period from Day -28 to Day -1, eligible subjects will begin the investigational treatment (ruxolitinib) on Cycle 1 Day 1 and will be treated for up to a maximum of 3 years (39 cycles/ 156 weeks) or until early discontinuation. Subjects who discontinue ruxolitinib for any reason earlier than 39 cycles will be followed every 6 months until 3 years from their first dose of ruxolitinib is reached. Refer to [Section 8.2.1](#) for details of the treatment period study visits. All subjects continuing to receive ruxolitinib treatment benefit following 3 years of treatment will be given the possibility to continue ruxolitinib outside the study, from another source, where permitted in accordance to local laws and regulations.

The ruxolitinib dose is based on the preliminary efficacy and safety data generated with this dose in subjects with steroid-refractory graft vs. host disease (SR-GvHD) ([Zeiser et al 2015](#)), and based on PK/safety data generated from the Phase III trials CINC424C2301 and CINC424D2301. As subjects ≥ 12 y to < 18 y are already being treated with 10 mg BID in CINC424D2301, this dose is the recommended phase II dose (RP2D), and will be used to treat all subjects in this age group.

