9.1 Discontinuation

9.1.1 Discontinuation of study treatment

Discontinuation of investigational treatment for a subject occurs when treatment is stopped earlier than the protocol planned duration, and can be initiated by either the subject or the investigator.

The investigator must discontinue investigational treatment for a given subject if, he/she believes that continuation would negatively impact the subject's well-being.

In addition to mandatory investigational treatment discontinuation listed in [Table 6-3](#), investigational treatment must also be discontinued under any of the following circumstances:

- Lack of efficacy of chronic GvHD treatment ([Section 16.4](#)).
- Lack of clinical benefit according to the Investigator.
- Underlying disease recurrence, or relapse ([Section 8.3.1.3](#)).
- Evidence of graft failure necessitating rapid taper of immunosuppression, administration of non-scheduled DLI, stem cell boost and/or chemotherapy, or other treatment that would expectedly affect chronic GvHD ([Section 8.3.2](#)).

- The following deviations from the prescribed dose regimen for investigational treatment:
- Dose hold > 21 days for ruxolitinib ([Section 6.5.1](#)).
- Adverse events leading to investigational treatment discontinuation. ([Section 6.5.1](#)).
- Pregnancy ([Section 8.4.2](#))
- Protocol deviation that results in a significant risk to the subject's safety including use of prohibited treatment ([Section 6.2.2](#)).

Subjects who discontinue ruxolitinib should NOT be considered withdrawn from the study. The subject should return for the early discontinuation follow-up assessments as indicated in [Table 8-1](#). Assessments will include:

- Height and weight
- Tanner staging (if appropriate)
- Graft failure assessment
- Hematologic underlying disease relapse/progression assessment
- Infection monitoring
- Second primary malignancy assessment
- Survival follow-up

The follow-up for subjects that permanently discontinue ruxolitinib early includes visits every 6 months until the subject reaches 3 years (39 cycles) from the date of their first ruxolitinib dose (see [Table 8-1](#)). In case the time between treatment discontinuation and 3 years (39 cycles) from the date of the first ruxolitinib dose is less than 6 months, subjects will be required to return for the one final early discontinuation follow-up visit as per [Table 8-1](#).

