2. On-treatment period: from day of first dose of ruxolitinib to 30 days after date of last actual administration of assigned treatment.
3. ***post-treatment period***: starting at Day 31 after last administration of ruxolitinib.

Safety summaries (tables, figures) include only data from the on-treatment period with the exception of baseline data which will also be summarized where appropriate (e.g. change from baseline summaries). In addition, a separate summary for death including on-treatment and post-treatment deaths will be provided. In particular, summary tables for adverse events (AEs) will summarize only on-treatment events, with a start date during the on-treatment period (***treatment-emergent*** AEs).

However, all safety data (including those from the post-treatment period) will be listed and those collected during the pre-treatment and post-treatment period will be flagged. In analyses for the safety disclosure, all AEs collected in the post-treatment period will be included and reported separately.

Subjects who taper off ruxolitinib due to achieving a CR or PR continue efficacy and safety assessments until their EoT visit which may be only after Cycle 39 unless the subject discontinues from study earlier. Safety data from these patients collected after the last study drug intake date + 30 days and before EoT visit will not be included in any safety analyses based on the on-treatment period as defined above. Nevertheless, these data will be listed and flagged in all listings (AEs, lab, vital signs). Subject who tapered off ruxolitinib are identified as they have reason "responder" for ruxolitinib permanent discontinuation on the exposure CRF.

For subjects who tapered off study treatment and later re-started ruxolitinib treatment after a cGvHD recurrence, the on-treatment period is from date of first dose of ruxolitinib to very last dose + 30 days including the period without treatment, which are collected in the database as dose interruption. Safety data (e.g. AEs, labs) collected during this period without treatment will be included in the summary tables as treatment emergent events.

Windows for multiple assessments

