2.8.4.5 Development (Growth and sexual maturation)

Growth

Graphical displays of percentile of height and weight over time will be provided for signal detection of impact on growth development. In case of a signal, further analyses may be provided.

In addition, a shift tables for height, weight, and BMI will be provided using following low/normal/high/(low and high) classification to compare baseline to the worst on-treatment value. Low: below the 5th percentile, Normal: between 5th and 95th percentiles, High: above the 95th percentile. Percentiles are based on CDC Growth Charts, derivation is described below.

Height and BMI will be summarized at 6-month intervals, using the standard deviation scores (SDS, also called z-score), velocity and velocity SDS as appropriate. The relevant height and weight values for each 6-month period are defined using time windows, according to [Table 2-1](#). The z-scores will allow identification of potential outliers.

SDS will be calculated using the current formulae provided by the CDC as follows:

$$\text{Calculate } z_{\text{ind}} = \frac{\left(\frac{x}{M}\right)^L - 1}{LS}$$

where:

- X is height in centimeters or BMI in kilograms/m²,
- L, M and S are height or BMI-, sex- and age-specific reference values from the CDC Growth Charts.

The CDC Height-for-age and BMI-for-age L, M and S reference values for males and females are available under <https://www.cdc.gov/growthcharts>. The age category immediately above the patient's exact age should be used. SDS is actually a Z score that measures the distance from the population mean in units of standard deviations. That is, SDS < 0 refers to values lower than the population mean, and for example SDS ≤ -1.645 refers to values in the lowest 5%. The percentile can be derived from the z-score by a normal distribution.

Height velocity is defined as follows:

Height velocity (cm/6-months) = (height in time window k – height in time window $k-1$) \div ([assessment date in time window k – assessment date in time window $k-1$] \div [365.25/2]),

and similarly for weight velocity.

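### Post-treatment growth and second-malignancy data are collected to 3 years from first dose, but the main safety summaries stop at last dose + 30 days and no planned analysis gives the promised second-malignancy rate

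*Protocol*

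**What the plan says.** **Collection.** Protocol 9.1.1 lists height and weight, Tanner stage where relevant, and second primary malignancy among the assessments for subjects who stop ruxolitinib early. This follow-up "includes visits every 6 months until the subject reaches 3 years (39 cycles) from the date of their first ruxolitinib dose".

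**Stated intention.** Protocol 4.5 (Long-Term Follow-Up) says that second primary malignancy rates "will be assessed during long-term follow up after transplant and will be compared with relevant epidemiologic data". In its pediatric safety text, the same section judges skeletal effects to be reversible but cautions that "post-treatment bone development may not fully compensate for the retardation".

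**Analysis window.** SAP 2.1.1 runs the on-treatment period from first dose to 30 days after last dose, and then states: "Safety summaries (tables, figures) include only data from the on-treatment period with the exception of baseline data". Protocol 12.5.2 has the same rule, and SAP 2.8 repeats it. It is applied to adverse events (SAP 2.8.1), events of special interest (2.8.1.2) and vital signs, which include height and weight (2.8.4.2). The shift tables for height, weight and BMI in SAP 2.8.4.5 are defined "to compare baseline to the worst on-treatment value". The 6-month height and BMI summaries take their windows from SAP Table 2-1, whose visit rows sit under an on-treatment heading. The percentile plots state no window, so the general rule governs them.

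**Exceptions.** The disclosure tables report post-treatment events separately (SAP 2.8.1.1). The all-deaths summary includes post-treatment deaths (2.8.2). All safety data are listed and flagged (2.1.1). The sexual-maturation figures use every available observation (2.8.4.5).

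**The concern.** Second cancers and recovery of growth are both outcomes for which the time after stopping matters. The study pays to collect that time, and the main summaries then leave it out.

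For malignancies, a stated intention has no analysis behind it: the SAP names no rate, no denominator and no comparator. For growth, a summary that ends 30 days after the last dose cannot show whether a child caught up, which is the point on which Protocol 4.5 itself expresses doubt.

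The same cut applies to responders who taper off and do not restart. They stay on the full visit schedule, but under SAP 2.1.1 their data beyond last dose + 30 days are listed only. At stake is an incomplete account of late safety in a pediatric study, not the primary efficacy result.

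**Working it through.** **1. Horizon.** Protocol 3 and 9.1.1 give 39 cycles, and Protocol 8.2.1 gives 28 days per cycle. 39 × 28 = 1092 days; 1092 / 7 = 156 weeks; 1092 / 365.25 = 2.99 years. This reproduces the stated 156 weeks and 3 years, counted from first dose.

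**2. Time outside the window, per child.** With last dose on day d and follow-up to day 1092, excluded days = 1092 − (d + 30), and off-drug follow-up in months = (1092 − d) / 30.4375.

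| Last dose | Off-drug follow-up | Excluded days | Share of 1092 |
|---|---|---|---|
| Day 169 (Cycle 7 Day 1) | 30.3 months | 893 | 82% |
| Day 365 | 23.9 months | 697 | 64% |
| Day 730 | 11.9 months | 332 | 30% |
| All 39 cycles completed | 0 | 0 | 0% |

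**3. Whole cohort.** The protocol's Amendment 2 summary gives 46 enrolled. If all are followed to day 1092, total time is 46 × 1092 / 365.25 = 137.5 patient-years. If a share s stops at day d and the rest complete, the excluded share is s × (1092 − d − 30) / 1092. The documents give no discontinuation rate, so s and d are assumptions:

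- s = 25%, day 730: 0.25 × 332 / 1092 = 7.6% (10.5 patient-years)
- s = 50%, day 365: 0.50 × 697 / 1092 = 31.9% (43.9 patient-years)
- s = 75%, day 169: 0.75 × 893 / 1092 = 61.3% (84.3 patient-years)

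Deaths and losses to follow-up would lower these figures.

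**4. Where a post-treatment second cancer would appear.** Protocol 8.4.1.7 makes it an adverse event, and 10.1.2 makes new malignant neoplasms serious. Once recorded as an adverse event, it enters the post-treatment disclosure table and the listings and, if fatal, the deaths summary. It does not enter the main adverse event, serious adverse event or special-interest tables. Capture may also be incomplete: Protocol 10.1.3 asks for reports of serious events after the 30-day period only when a causal link is suspected. A cancer judged unrelated would then depend on the 6-monthly malignancy assessment and the adverse event page.

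**5. Where post-treatment height and weight would appear.** In listings only. No exception matches the one for Tanner figures.

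**6. Is a denominator available?** Yes. SAP 2.4.1 defines duration of follow-up from first dose to last contact, but no safety rate uses it.

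**The case against.** The best defence is that an on-treatment window is an ordinary choice for attribution. Children who stop without response are treated by institutional practice (Protocol 6.1.5), so later events are confounded by other therapy. With 46 children, any second cancers are likely to be few, and a flagged listing shows each one. The protocol's second-malignancy endpoint in Table 2-1 is occurrence under adverse event monitoring; the epidemiologic comparison stands only in the risk narrative. On growth, Protocol 4.5 expects the largest effect below age 2. The 46 enrolled include no child that young, and 22 were 12 or older, an age equivalent at which animals showed no bone effect.

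Much of this stands, and it rules out several stronger readings that a reader might infer:

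- *Follow-up lasts 3 years after stopping.* It ends 3 years from first dose, so off-drug time is what remains of that period.
- *The SAP departs from the protocol.* Protocol 12.5.2 contains the same rule; the tension is with Protocol 4.5.
- *Post-treatment cancers vanish from every table.* The disclosure and deaths tables are real exceptions.
- *The epidemiologic comparison covers growth.* That sentence concerns second primary malignancies only. The growth point rests on the caution about incomplete recovery and on the data collected.
- *The cut-off flatters the drug.* On-treatment malignancy counts cannot exceed all-follow-up counts, but growth could go either way: a worst on-treatment value hides recovery as readily as a lasting deficit.

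The defence does not answer the rest. Confounding is a reason to show both windows side by side. A listing is not a rate. The other 24 children (17 aged 6 to under 12, 7 aged 2 to under 6) are below 12. The growth exclusion is explicit only for vital signs and the shift tables, and follows from the general rule and Table 2-1 for the plots and score summaries; that ambiguity should itself be closed.

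**Conclusion.** The point holds in this limited form. Following the plan leaves the late-safety account incomplete: there is no second-malignancy rate over all follow-up, no epidemiologic comparison, and no summary of growth after stopping.

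The size is uncertain. About 8% to 61% of patient-time falls outside the window, assuming that 25% to 75% stop between day 730 and day 169 and that all are followed to day 1092. A narrower figure might be inferred, such as 25% to 39% from assuming that 40% to 60% stop at about 12 months, but nothing in the documents supports that stopping rate. The per-child shares in the table need only a last-dose date and follow-up to day 1092.

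Many second cancers would fall outside any window here. Protocol 4.5 itself places skin cancers and melanoma generally 10 to 15 years after transplant, so the remedy makes the study's own data complete and does not settle long-term risk.

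**What to change.** 1. **Second primary malignancy.** Report the count and the rate per patient-year from first dose to last contact, using the follow-up duration already defined in SAP 2.4.1, with an exact confidence interval. Place it beside the on-treatment figure, and name the epidemiologic comparator that Protocol 4.5 calls for. Take cases from the malignancy assessment as well as the adverse event page.
2. **Growth plots and score summaries.** State in SAP 2.8.4.5 that the height and weight percentile plots and the 6-month height and BMI summaries use all available data with off-drug time marked, as for the Tanner figures. The 6-monthly visits need their own windows: from Cycle 9, Table 2-1 windows span 29 days (for example 211 to 239) in every 84, so such a visit can fall in none.
3. **Shift tables.** Keep the on-treatment version, and add a shift from baseline to last available value.

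The cost is a few extra tables and figures from data already collected, with no change to conduct. The rate will be imprecise and confounded by later therapy, and the report should say so. For example, zero events in 137.5 patient-years would still leave an upper 95% limit of −ln(0.025) / 137.5 = 3.69 / 137.5, or about 2.7 per 100 patient-years.
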